### 3.1.2 Key secondary endpoint

Using a hierarchical testing procedure for familywise 2-sided type I error control at 0.05, the hypothesis test in key secondary analysis on 4-week CFR will be performed if and only if null hypothesis in primary analysis is rejected. The conditional power for detecting a 50% drop of 4-week CFR are evaluated under different assumptions on control arm 4-week CFR.

**Table 3-2 Power for key secondary analysis (sample size = 450)**

CFR (%)		Clinically meaningful benefits			Power (2-side $\alpha=0.05$ )
Control	ACZ885	Difference	OR	RR	
25	12.5	-12.5	0.43	0.5	92%
20	10	-10	0.44	0.5	83%

15	7.5	-7.5	0.46	0.5	70%
----	-----	------	------	-----	-----

Cases of lost to follow up before patient's recovery (clinical status = 0 or 1 on the 9-point ordinal scale) and before Day 29 is expected to be minimal. Sample size adjustment for key secondary analysis is not planned.

## 4 Change to protocol specified analyses

No changes on the primary analyses for the primary and key secondary endpoints that are pre-specified on the protocol.

The following analyses are not specified on the protocol but added and specified on the SAP to address comments from various health authority comments on the protocol:

- Sensitivity analysis comparing the rate difference between treatment arms using the marginal standardization method has been added to both the primary and key secondary endpoints.
- A supplementary analysis considering any patients who discontinued from study or lost to follow-up as non-survivors is added for the key secondary endpoint.

■ [REDACTED]  
■ [REDACTED]

## 5 Appendix

### 5.1 Imputation rules

#### 5.1.1 Study drug

Missing or partial dates are not allowed, therefore, no imputation will be made to the study treatment date.

#### 5.1.2 AE date imputation

For the start and end dates of the adverse event records, when incomplete or missing, dates will be imputed according to Novartis standards as described below.

##### 5.1.2.1 AE end date imputation

Incomplete or missing AE end date will be dealt with in the following way:

1. If the AE end date month is missing, the imputed end date should be set to the earliest of the (31DECYYYY, date of death).
2. If the AE end date day is missing, the imputed end date should be set to the earliest of the (last day of the month, date of death).
3. If AE year is missing or AE is ongoing, the end date will not be imputed.

4. If the imputed AE end date is less than the existing AE start date then use AE start date as AE end date.

### 5.1.2.2 AE start date imputation

The following table explains the notation used in the logic matrix. Please note that completely missing start dates will not be imputed.

	Day	Month	Year
Partial Adverse Event Start Date	Not used	MON	YYYY
Treatment Date	Not used	TRTM	TRTY

The following matrix explains the logic behind the imputation.

	MON MISSING	MON < TRTM	MON = TRTM	MON > TRTM
YYYY MISSING	(1) No convention	(1) No convention	(1) No convention	(1) No convention
YYYY < TRTY	(2.a) Before Treatment Date	(2.b) Before Treatment Date	(2.b) Before Treatment Date	(2.b) Before Treatment Date
YYYY = TRTY	(4.a) Uncertain	(4.b) Before Treatment Date	(4.c) Uncertain	(4.c) After Treatment Date
YYYY > TRTY	(3.a) After Treatment Date	(3.b) After Treatment Date	(3.b) After Treatment Date	(3.b) After Treatment Date

Before imputing AE start date, find the AE start reference date.

1. If the (imputed) AE end date is complete and the (imputed) AE end date < treatment date then AE start reference date = min (informed consent date, earliest visit date).
2. Else AE start reference date = treatment date

Impute AE start date -

1. If the AE start date year value is missing, the date uncertainty is too high to impute a rational date. Therefore, if the AE year value is missing, the imputed AE start date is set to NULL.
2. If the AE start date year value is less than the treatment date year value, the AE started before treatment. Therefore:
  - a. If AE month is missing, the imputed AE start date is set to the mid-year point (01JulYYYY).
  - b. Else if AE month is not missing, the imputed AE start date is set to the mid-month point (15MONYYYY).
3. If the AE start date year value is greater than the treatment date year value, the AE started after treatment date. Therefore:
  - a. If the AE month is missing, the imputed AE start date is set to the year start point (01JanYYYY).
  - b. Else if the AE month is not missing, the imputed AE start date is set to the later of (month start point (01MONYYYY), AE start reference date + 1 day).

4. If the AE start date year value is equal to the treatment date year value:
  - a. And the AE month is missing the imputed AE start date is set to the AE reference start date + 1 day.
  - b. Else if the AE month is less than the treatment month, the imputed AE start date is set to the mid-month point (15MONYYYY).
  - c. Else if the AE month is equal to the treatment date month or greater than the treatment date month, the imputed AE start date is set to the later of (month start point (01MONYYYY), AE start reference date + 1 day).

If complete (imputed) AE end date is available and the imputed AE start date is greater than the (imputed) AE end date, then imputed AE start date should be set to the (imputed) AE end date.

### **5.1.3 Concomitant medication date imputation**

For the start and end dates of the concomitant medication records, when incomplete or missing, dates will be imputed according to Novartis standards as described below. The same data imputation rules will be applied for therapies and procedures.

#### **5.1.3.1 Concomitant medication end date imputation**

Incomplete or missing end date for prior therapies will be dealt with in the following way

1. If the CM end date year value is missing, the date uncertainty is too high to impute a rational date. Therefore, if the CM end year value is missing or ongoing, the imputed CM end date is set to NULL.
2. Else, if the CM end date month is missing, the imputed end date should be set to the earliest of the (study end date, 31DECYYYY, date of death).
3. If the CM end date day is missing, the imputed end date should be set to the earliest of the (study end date, last day of the month, date of death).

If the imputed CM end date is less than the existing CM start date, use the CM start date as the imputed CM end date.

#### **5.1.3.2 Concomitant medication start date imputation**

In order to classify a medication as prior and prior/concomitant, it may be necessary to impute the start date.

Completely missing start dates will be set to one day prior to treatment date. As a conservative approach, such treatments will be classified as prior and concomitant (and summarized for each output).

Concomitant treatments with partial start dates will have the date or dates imputed.

The following table explains the notation used in the logic matrix

	Day	Month	Year
Partial CMD Start Date	Not used	MON	YYYY
Treatment Date	Not used	TRTM	TRY

The following matrix explains the logic behind the imputation.

	MON MISSING	MON < TRTM	MON = TRTM	MON > TRTM
YYYY MISSING	(1) Uncertain	(1) Uncertain	(1) Uncertain	(1) Uncertain
YYYY < TRTY	(2.a) Before Treatment Date	(2.b) Before Treatment Date	(2.b) Before Treatment Date	(2.b) Before Treatment Date
YYYY = TRTY	(4.a) Uncertain	(4.b) Before Treatment Date	(4.a) Uncertain	(4.c) After Treatment Date
YYYY > TRTY	(3.a) After Treatment Date	(3.b) After Treatment Date	(3.b) After Treatment Date	(3.b) After Treatment Date

1. If the CM start date year value is missing, the imputed CM start date is set to one day prior to Treatment date.
2. If the CM start date year value is less than the Treatment date year value, the CM started before treatment. Therefore:
  - a. If the CM month is missing, the imputed CM start date is set to the mid-year point (01JulYYYY).
  - b. Else if the CM month is not missing, the imputed CM start date is set to the mid-month point (15MONYYYY).
3. If the CM start date year value is greater than the Treatment date year value, the CM started after treatment. Therefore:
  - a. If the CM month is missing, the imputed CM start date is set to the year start point (01JanYYYY).
  - b. Else if the CM month is not missing, the imputed CM start date is set to the month start point (01MONYYYY).
4. If the CM start date year value is equal to the Treatment date year value:
  - a. And the CM month is missing or the CM month is equal to the Treatment date month, then the imputed CM start date is set to one day prior to Treatment date.
  - b. Else if the CM month is less than the Treatment date month, the imputed CM start date is set to the mid-month point (15MONYYYY).
  - c. Else if the CM month is greater than the treatment date month, the imputed CM start date is set to the month start point (01MONYYYY).

If complete (imputed) CM end date is available and the imputed CM start date is greater than the (imputed) CM end date, then imputed CM start date should be set to the (imputed) CM end date.

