### 2.2.1 Subgroup of interest

Subgroup analyses will be conducted to assess consistency of the treatment effect among the subgroups without multiplicity adjustments. The following subgroups will be evaluated for the primary endpoint, i.e. survival without ever requiring invasive mechanical ventilation from Day 3 (inclusive) up to Day 29 (inclusive).

- Age category (< 65, ≥ 65 years)
- Age category (12 - <18; 18 - <40; 40 - <65; 65 - <75; ≥75)
- Baseline clinical status based on 9-point ordinal scale (≤4, ≥5)
- Baseline body Weight (40 kg - <60 kg, 60 kg – 80 kg, >80 kg)
- Baseline BMI categories (≤ 30.0 kg/m^2 and > 30.0 kg/m^2)
- Sex (male, female)
- Race (White, Asian, Black, other)
- Ethnicity: Hispanic, non-Hispanic
- Region (North America, Russia, Rest of Europe)
- Active comorbidities based on Medical History
  - Cerebrovascular disease (Yes, No)
  - Chronic heart disease (Yes, No)
  - Hypertension (Yes, No)
  - Diabetes (Yes, No)
  - Asthma (Yes, No)
  - COPD (Yes, No)
  - Chronic kidney disease (Yes, No)
  - Malignant neoplasm (Yes, No)
  - Liver disease (Yes, No)

- Use of dexamethasone >= 6 mg/day or equivalent or not (Yes, No)
- Use of remdesivir or not (Yes, No)
- Use of convalescent plasma/serum or not (Yes, No)
- Use of hydroxychloroquine or not (Yes, No)
- Use of azithromycin or not (Yes, No)
- Use of JAK inhibitor or not (Yes, No)
- Use of Heparin or not (Yes, No)

- Use of anti-IL6 treatment (Yes, No)

The subgroups based on the use of prior COVID-19-induced pneumonia treatment medication are defined as with/without the given medication that started on or after the onset of the first symptom of COVID-19-induced pneumonia and before the study treatment date (or randomization date if no study treatment is taken).

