#### **5.1.4 Concomitant therapies and procedures date imputation**

The missing dates will be imputed using the same rule as for the concomitant medication.

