**Table 5-4 Type of pulmonary/Ventilatory support based on the level of oxygen requirement from low to high**

Type of support	Require supplemental oxygen	Require mechanical ventilation
Low flow nasal oxygen	Yes	No
High flow nasal oxygen	Yes	No
Oxygen via face mask	Yes	No
Non-invasive ventilation	Yes	No
Mechanical ventilation	Yes	Yes
Intubation	Yes	Yes
Tracheostomy	Yes	Yes

Type of support	Require supplemental oxygen	Require mechanical ventilation
ECMO	Yes	Yes

The baseline use of pulmonary ventilatory support is the latest type of Oxygen supply that started before the study treatment. There are records with an oxygen supply starting from Day 1 but there is no time information provided, in which case, it is not possible to tell if such procedure started pre-/post-treatment. Here is the summary on how to define baseline when time information is missing from a procedure that starts/ends on Day 1:

- If a patient is on type A oxygen supply from a pre-treatment date and end on Day 1 then changed from type A to type B on the same date, type A will be considered as the baseline type of oxygen supply.
- If a patient has one record on oxygen supply that ends on Day 1 but with one record starting on Day 1, the perspective oxygen supply type will be considered as the baseline.

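### A medication or procedure start with an unknown day in the dosing month is set to the day before dosing, so a post-dose record can define a prior-use subgroup or baseline support (minor)

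*SAP*

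**What the plan says.** SAP 5.1.3.2 fills in partial medication start dates. When the year is the dosing year and the month is missing, or when the "CM month is equal to the Treatment date month, then the imputed CM start date is set to one day prior to Treatment date" (rule 4a). A start with no year, including a completely missing start, also goes to the day before treatment (rule 1). The SAP's own logic table marks these cells as uncertain.

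The rules reach beyond drugs. SAP 5.1.3 adds: "The same data imputation rules will be applied for therapies and procedures". SAP 5.1.4 repeats it: "The missing dates will be imputed using the same rule as for the concomitant medication".

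Two definitions then read the start date:

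- SAP 2.2.1 places a patient in the Yes level of a prior-medication subgroup (dexamethasone, remdesivir, JAK inhibitor, anti-IL6 and others) if the drug "started on or after the onset of the first symptom of COVID-19-induced pneumonia and before the study treatment date".
- SAP 5.6: "The baseline use of pulmonary ventilatory support is the latest type of Oxygen supply that started before the study treatment". Its special provisions are introduced by: "Here is the summary on how to define baseline when time information is missing from a procedure that starts/ends on Day 1". They deal with a missing clock time on Day 1, not with a missing start day.

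For adverse events, SAP 5.1.2.2 rule 4c resolves the same uncertainty the other way: "the imputed AE start date is set to the later of (month start point (01MONYYYY), AE start reference date + 1 day".

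**The concern.** This is a single-dose trial with a four-week primary window, so many post-dose starts share a calendar month with the dose. Rule 4a moves every one of them that lacks a day to Day -1. Such a start precedes dosing and, in a patient already hospitalized with pneumonia, would normally follow symptom onset. It therefore meets the SAP 2.2.1 definition of prior use. For respiratory support, a start on Day -1 will usually be the latest one before dosing, so it can displace the patient's true baseline type.

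At stake is whether these variables are really baseline variables. Starting a new drug or escalating oxygen after dosing is partly an outcome. A subgroup that includes such patients conditions on post-randomization information, and the subgroup odds ratios in the forest plots of SAP 2.5.6 become harder to interpret. A few records could matter most in the anti-IL6 subgroup. Protocol 5.2 criterion 3 excludes recent immunomodulators, tocilizumab among them, so true prior use should be rare.

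**Working it through.** The plan states no figure on this point, so there is none to reproduce. The check applies the rules to example dates and then asks how often a post-dose start shares the dosing month.

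**1. The rules applied.** Dates are assumed, all in 2020, with the day of the start unknown. Study day follows SAP 2.1.1: date minus Day 1, plus 1 on or after dosing; date minus Day 1 before dosing.

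| Dosed | True start | True day | Medication/procedure rule gives | AE rule gives |
|---|---|---|---|---|
| 4 May | 12 May | 9 | 3 May, Day -1 (4a) | Day 2 |
| 10 June | 25 June | 16 | 9 June, Day -1 (4a) | Day 2 |
| 1 May | 20 May | 20 | 30 April, Day -1 (4a) | Day 2 |
| 28 May | 3 June | 7 | 1 June, Day 5 (4c) | Day 5 |

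In the first three rows a post-dose start becomes pre-dose. The third row is wrong whatever the true day, because 30 April lies outside the recorded month of May. This happens to every patient dosed on the 1st who has a same-month start with no day. In the fourth row the start falls in the next month and stays post-dose.

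**2. How often a post-dose start shares the dosing month.** Assume dosing dates uniform over a 30-day month and true starts uniform over the H days after dosing. The day k days after dosing is in the same month with probability (30 - k)/30. Averaging over k = 1 to H gives 1 - (H + 1)/60:

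- H = 7 (Days 2-8): 1 - 8/60 = 0.867
- H = 14 (Days 2-15): 1 - 15/60 = 0.750
- H = 28 (Days 2-29): 1 - 29/60 = 0.517

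Using the real calendar for May to August, again with uniform dates, the shares are 89% for Days 2-7, 77% for Days 2-14 and 53% for Days 2-29. Among the Day 2-29 starts that would be backdated, the mean shift is about 11 days and the largest 29.

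**3. What the rule does not reach.**

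- The primary endpoint is derived from the 9-point ordinal scale (Protocol 12.4.1), scored daily in hospital (Protocol 8.3.1). The key secondary model adjusts for baseline ordinal status (SAP 2.6.2), and SAP 5.3.2 says the primary model is the same. No imputed procedure date enters either.
- SAP 2.4.2.1 calls a drug prior only if it stopped before dosing. The end-date rules in SAP 5.1.3.1 move a partial end date late, to the end of the month or year unless the study end or death comes first, or leave it empty. A drug truly used after dosing is thus never given a stop date before dosing, and it stays concomitant in that summary.

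**The case against.** The strongest reply is that few records can be affected. Medications and oxygen are recorded daily in hospital (Protocol Table 8-1), missing values are queried (Protocol 11.2), and the only timing gap that SAP 5.6 reports is a missing clock time on Day 1. After discharge, medications are collected by phone, where an unknown day is more plausible, but the documents give no count. This reply stands and limits the weight of the point.

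A second reply is that both date conventions are stated sponsor standards. Treating an uncertain AE as treatment-emergent is cautious for safety, so the contrast with the medication rule is not a contradiction. That also stands. Simply adopting the AE convention would have its own defect: treatment date plus one leaves the recorded month for anyone dosed on its last day.

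Third, the rule acts alike in both arms under blinding. That is true, but it does not make a post-dose event a baseline characteristic.

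Fourth, no legible analysis uses the baseline type from SAP 5.6. Other uses may lie in blacked-out sections and cannot be judged. A backdated intubation would also stand out against Protocol 5.2 criterion 2, whereas oxygen escalation or a drug would not.

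A reader might go further and infer that use of rescue drugs is under-reported, or that post-dose escalation drops out of efficacy follow-up. The documents support neither. The medication summary turns on the stop date, completely missing starts are counted under both headings, and escalation enters efficacy through the ordinal scale.

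**Conclusion.** Wrong as written, minor. Rule 4a, together with rule 1, lets a record that truly began after dosing define a prior-use subgroup of the primary endpoint or the baseline support type. For patients dosed on the 1st it yields an impossible date whenever the month is known and the day is not. The effect is confined to the exploratory subgroup forest plots, which carry no multiplicity adjustment, and to the baseline support variable.

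The shares of roughly 52% to 87% might be read as misclassification rates. They are not. They apply only to unknown-day records that truly started after dosing, and they rest on uniform dates. The share of unknown-day records that are truly post-dose is not known, and for drugs started around admission it could be low. The number of patients affected cannot be computed from the documents.

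**What to change.** - State in SAP 2.2.1 and 5.6 that a start date imputed under rule 1 or 4a may not by itself define a prior-use subgroup or baseline support. Count such a record as pre-dose only when other recorded data show it, for example an end date before dosing.
- For support, check the record against the Day 1 pre-dose ordinal score, and query any baseline invasive ventilation against Protocol 5.2 criterion 2.
- In SAP 5.1.3.2, keep the imputed date within the recorded month.
- Reconcile SAP 5.1.3.2, which counts a drug with a completely missing start as both prior and concomitant, with SAP 2.4.2.1, which allows each drug only one class.

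The cost is a few sentences and a small program change. The downside is that a few true pre-dose starts with an unknown day would not be counted as prior use.

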#### **5.1.4 Concomitant therapies and procedures date imputation**

The missing dates will be imputed using the same rule as for the concomitant medication.

## 5.2 AEs coding/grading

AEs are coded using the MedDRA terminology. The latest version of MedDRA will be used and will be specified on the footnote of relevant output.

AEs grade are assessed by investigators and captured on the AE CRF based on three levels: mild, moderate, and severe.

## 5.3 Statistical models

### 5.3.1 Primary analysis

The image consists of several horizontal black bars of varying lengths and positions. A central cluster of bars is located in the middle-left area, with a small gap between the top and bottom rows. To the left of this cluster, there is a long, thin horizontal bar. To the right, there is a very long horizontal bar that spans most of the width of the image. Below the central cluster, there is a long horizontal bar. At the very bottom of the image, there is a very long horizontal bar that extends across the entire width. The bars are rendered in black against a white background.

### 5.3.1.1 Sensitivity analysis of the primary endpoint

the first time in the history of the world, the people of the United States have been called upon to determine whether they will submit to the law of force, or the law of the Constitution. We shall not shrink from that great responsibility. We shall meet the question in a spirit of firm determination, and with a sense of duty to our country and to the world.

### 5.3.2 Key secondary analysis

The null hypothesis for the key secondary analysis is that there is no difference in the COVID-19 related death rate (i.e. CFR) in patients treated with canakinumab compared to placebo. The alternative hypothesis is that there is a difference between the two treatment groups.

The statistical superiority test based on odds ratio will be performed to compare the CFR between canakinumab and placebo arms and the same logistic regression model as described for the primary analysis will be used.

Same sensitivity analysis using the marginal standardization method as for the primary endpoint will also be provided for the key secondary endpoint.

## 5.4 Rule of exclusion criteria of analysis sets

**Table 5-1 Protocol deviations that cause subjects to be excluded**

Deviation ID	Description of Deviation	Exclusion in Analyses
INCL01	Informed consent not obtained	Excluded from FAS, Safety set

**Table 5-2 Subject Classification**

Analysis Set	PD ID that cause subjects to be excluded	Non-PD criteria that cause subjects to be excluded
Enrolled	INCL01	
FAS	INCL01	Not Randomized
Safety set	INCL01	No double-blind study drug taken

## 5.5 Clinical status (9-point ordinal scale)

Assessment of clinical status using a 9-point ordinal scale ([WHO 2020](#)) will be recorded at baseline on Day 1 and then again once daily every morning till discharge from the hospital or Day 29. Each day, the worse score for the previous day will be recorded (i.e. on Day 3, Day 2 score is obtained and recorded as Day 2). The description for each score level is specified in Table 5-3.

There are cases that site may report two 9-point status assessments on early discharge visit or early discontinuation visit:

- one assessment is captured as the worst assessment on the day of early discharge/discontinuation visit and entered under the visit of Day X (X=early discharge/discontinuation date-Day 1+1)
- one assessment is captured as the status by the time of early discharge/discontinuation and entered under the visit of early discharge/discontinuation

In summary by visit, the worse score will be used for the summary on Day X and the score reported for early discharge/discontinuation will be used for data imputation with LOCF and other analyses based on the latest status by early discharge/discontinuation.

